16.2 Sample Size/Accrual Rate

16.21 Sample Size: A total of 25 evaluable Cohort 1 and 25 evaluable Cohort 2 patients will be accrued per study design (50 evaluable total), unless one or both cohorts of the study are permanently closed at the stage 1 analysis or undue

toxicity is observed. We anticipate accruing an additional 10 patients (5 Cohort 1, 5 Cohort 2) in order to account for ineligibility, cancellation, major treatment violation, or other reasons. Therefore, maximum accrual is 60 patients for this trial (30 for each Cohort).

16.22 Accrual Time and Study Duration: We expect to accrue about 3 patients per month to this trial. Therefore, the accrual period for this Phase II study is expected to be about 20 months. We anticipate that the study will take approximately 3 years to complete. This allows a 6 month follow-up for the final patient enrolled, along with data entry, data clean-up, and analysis.

16.3 Analysis of Secondary Endpoints for both Cohorts.

This study will assess multiple secondary endpoints, including adverse events, progression-free survival (PFS) and overall survival (OS). All these analyses will be done for each cohort separately. In addition, all primary/secondary data will be summarized by descriptive factors as well (i.e. prior treatment, etc.).

16.31 Adverse Events: All patients that have initiated treatment will be considered evaluable for assessing adverse events. The maximum grade for each type of adverse event will be recorded for each patient, and frequency tables will be reviewed to determine adverse event patterns. Only the grade 2+ adverse events will be assessed, regardless of relationship to the study treatment.

16.32 Progression-Free Survival (PFS): Defined as the time from registration to the first of either death due to any cause or progression. The distribution of PFS will be estimated using the method of Kaplan-Meier.

16.33 Overall Survival: Defined as the time from registration to death due to any cause. The distribution of survival time will be estimated using the method of Kaplan-Meier. Special attention will be paid to any registered patient who dies early (i.e., within 60 days) of initiating their treatment. Circumstances surrounding such early deaths will be classified as being either due to malignant disease, toxicity, other causes, or of unknown reasons.

16.4 Laboratory Correlative Studies (all done by Cohort): All analyses with respect to the translational component of this study are intended to be hypothesis-generating and descriptive in manner. Clinical data (i.e. CR rates confirmed response rates, PFS, OS, etc.) will be correlated with tumor marker data of interest (CD8+, PD-L1, PD-L2, T cell functional capacity markers, anti-thyroglobulin antibody levels, tumor mutation status, and other markers). The Chi-Square (or Fisher's Exact test) will be used to assess the association of categorical clinical data with categorical biomarker data. Time-to-event clinical data (PFS, OS) will be correlated with biomarker data using Kaplan-Meier methodology and Cox regression models. Logistic regression models will also be used to predict binary clinical data with baseline biomarker data. Finally, graphical methods and descriptive statistics will be used to summarize the data as well. Two-sided p-values < 0.05 will be considered statistically significant.

16.5 Adverse Event Stopping Rule:

- 16.51 Monitoring: The principal investigator and the study statistician will review the study periodically (at least twice a year) to identify accrual, toxicity, and any endpoint problems that might be developing. The trial is monitored continually by the study team who are notified of every grade 4 and 5 event in real time. The Mayo Clinic Cancer Center (MCCC) Data Safety Monitoring Board (DSMB) is responsible for reviewing accrual and safety data for this trial at least twice a year, based on reports provided by the MCCC Statistical Office.
- 16.52 Adverse Event Stopping Rule: The stopping rule specified below is based on the knowledge available at study development. We note that the Adverse Event Stopping Rule may be adjusted in the event of either (1) the study re-opening to accrual after any temporary suspension or (2) at any time during the conduct of the trial and in consideration of newly acquired information regarding the adverse event profile of the treatment(s) under investigation. The study team may also choose to suspend accrual because of unexpected adverse event profiles that have not crossed the specified rule below. We expect approximately 10% of patients to experience grade 4+ adverse events (at least possibly related to study medication). In this study, we will suspend accrual to allow for a full review of the data, if any of the following occur in each cohort separately:
- If at any time, 3 of the initial 10 patients (or 30% of all patients when accrual is greater than 10) have experienced any grade 4 adverse event (at least possibly related to the study medication).
 - If at any time, 1 of the initial 10 patients (or 10% of all patients when accrual is greater than 10) have experienced any grade 5 adverse event (at least possibly related to the study medication).
- 16.6 Accrual Monitoring Stopping Rule
Given the expected accrual rate is around 3 patients per month, it is expected that the study will take around 20 months to fully accrue. We plan to monitor the accrual continually and if we only end up accruing 5 patients or less in the first year (after study activation), we will consider stopping the trial for slow accrual.
- 16.7 Primary Endpoint Completion Time Estimation (For clinicaltrials.gov reporting):
The primary endpoint is the complete response (CR) rate for Cohort 1 and the confirmed response rate for Cohort 2. The final analysis is expected to take place around 36 months after the study begins, so we expect the primary endpoint completion time to be around 36 months after study activation.
- 16.8 Inclusion of Women and Minorities
- This study will be available to all eligible patients, regardless of race, gender, or ethnic origin. There is no information currently available regarding differential effects of this regimen in subsets defined by race, gender, or ethnicity, and there is no reason to expect such differences to exist. Based on prior studies involving similar disease sites, we expect about 10% of patients will be classified as minorities by race and about 50% of patients to be women. Expected sizes of racial by gender subsets are shown in the following table:

Accrual Targets			
Ethnic Category	Sex/Gender		
	Females	Males	Total
Hispanic or Latino	3	3	6
Not Hispanic or Latino	27	27	54
Ethnic Category: Total of all subjects	30	30	60
Racial Category			
American Indian or Alaskan Native	1	1	2
Asian	0	1	1
Black or African American	2	1	3
Native Hawaiian or other Pacific Islander	0	0	0
White	27	27	54
Racial Category: Total of all subjects	30	30	60

Ethnic Categories: **Hispanic or Latino** – a person of Cuban, Mexican, Puerto Rican, South or Central American, or other Spanish culture or origin, regardless of race. The term “Spanish origin” can also be used in addition to “Hispanic or Latino.”
Not Hispanic or Latino

Racial Categories: **American Indian or Alaskan Native** – a person having origins in any of the original peoples of North, Central, or South America, and who maintains tribal affiliations or community attachment.
Asian – a person having origins in any of the original peoples of the Far East, Southeast Asia, or the Indian subcontinent including, for example, Cambodia, China, India, Japan, Korea, Malaysia, Pakistan, the Philippine Islands, Thailand, and Vietnam. (Note: Individuals from the Philippine Islands have been recorded as Pacific Islanders in previous data collection strategies.)
Black or African American – a person having origins in any of the black racial groups of Africa. Terms such as “Haitian” or “Negro” can be used in addition to “Black or African American.”
Native Hawaiian or other Pacific Islander – a person having origins in any of the original peoples of Hawaii, Guam, Samoa, or other Pacific Islands.
White – a person having origins in any of the original peoples of Europe, the Middle East, or North Africa.

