- Investigator-assessed clinical benefit (e.g. absence of rapid disease progression and absence of progressive tumor at a critical anatomic site that requires urgent alternative intervention), and
- The patient is tolerating study drug.
- Patient does not continue to progress at 4 week follow-up imaging after PD first noted.

Patients with initial progression will be assessed with clinical judgment as to whether the patient is deriving clinical benefit from treatment and should continue study treatment or discontinue and enter the follow up/survival phase of the study. If progression is confirmed then the date of disease progression will be the first date the patient met the criteria for progression based on the standard RECIST 1.1 criteria.

13.7 A patient is deemed *ineligible* if after registration, it is determined that at the time of registration, the patient did not satisfy each and every eligibility criteria for study entry. The patient may continue treatment off-protocol at the discretion of the physician as long as there are no safety concerns, and the patient was properly registered. The patient will go directly to the event-monitoring phase of the study (or off study, if applicable).

- If the patient received treatment, all data up until the point of confirmation of ineligibility must be submitted. Event monitoring will be required per Section 18.0 of the protocol.
- If the patient never received treatment, on-study material must be submitted. Event monitoring will be required per Section 18.0 of the protocol.

13.8 A patient is deemed a *major violation*, if protocol requirements regarding treatment in cycle 1 of the initial therapy are severely violated that evaluability for primary end point is questionable. All data up until the point of confirmation of a major violation must be submitted. The patient will go directly to the event-monitoring phase of the study. The patient may continue treatment off-protocol at the discretion of the physician as long as there are no safety concerns, and the patient was properly registered. Event monitoring will be required per Section 18.0 of the protocol.

13.9 A patient is deemed a *cancel* if he/she is removed from the study for any reason before any study treatment is given. On-study material and Off-Treatment Form must be submitted. Event monitoring will be required per protocol (Section 18.0).

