16.0 Statistical Considerations and Methodology

16.1 Study Design/Endpoints

- 16.11 Background/Overview: This novel study will be the first to assess pembrolizumab and lenvatinib combination therapy in advanced DTC (and in any cancer). There is an ongoing basket trial (KEYNOTE-028 (NCT02054806)) that has enrolled patients with advanced thyroid cancer to a single agent pembrolizumab (200 mg iv every 3 weeks) study. Preliminary data from the thyroid cohort in this trial was presented at the 2016 American Society for Clinical Oncology (Mehnert JM, et al, J Clin Oncol 34, 2016 (suppl; abstr 6091)). The study enrolled 22 patients with DTC, with a median duration of follow-up of 74 weeks (29-87 weeks). No patients achieved a CR (0%) and 2 patients had a PR (9.1%), with 12 having SD (54%), which is why we will not have a pembrolizumab-only arm in this study. Our study will be done for 2 different cohorts (Cohort 1: Lenvatinib-naïve patients; Cohort 2: progressed on Lenvatinib alone). Both cohorts will receive the same combination therapy. The primary endpoint is different for the 2 cohorts, as described below (16.12 and 16.14). This study will also assess many secondary endpoints as well, as explained in detail below (16.3). Finally, this study will also assess important correlative science endpoints (16.4).
- 16.12 Overview and Primary Endpoint for Cohort 1: The complete response (CR) rate for lenvatinib alone was around 2%. The CR for patients with advanced DTC treated with pembrolizumab is 0% (see Section 16.11). A CR rate of around 15% would be clinically significant and worthy of further study. The primary endpoint for Cohort 1 is this CR rate (per RECIST 1.1 criteria). All patients meeting the eligibility criteria who have signed a consent form and have begun treatment will be considered evaluable for the primary endpoint. A patient that has a CR (Cohort 1) is considered a treatment “success”. The following one-stage binomial design (see below) requires 25 evaluable patients, and simultaneously discriminates between CR rates of 2% vs. 15%.
- 16.13 Decision Rules for Cohort 1:
- 16.131 Final Analysis Decision Rule: Enroll 25 total evaluable patients. If at least 2 patients have a success (at least 8%) among the 25 evaluable patients, this combination therapy would be considered worthy of further testing in this disease. If 0 or 1 patients have a success, this combination therapy will be considered negative and no further study would be warranted.

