- 16.132 Power and Significance Level: This design has 91% power to detect a

true success rate of 15%, with a significance level of 0.09 if the true success rate is 2%.

16.14 Overview and Primary Endpoint for Cohort 2: It is expected that the confirmed response rate is around 5% in this disease population. A confirmed response rate of around 25% would be clinically significant and worthy of further study. The primary endpoint for Cohort 2 is this confirmed response rate (per RECIST 1.1 criteria). All patients meeting the eligibility criteria who have signed a consent form and have begun treatment will be considered evaluable for the primary endpoint. A confirmed tumor response is defined to be a CR or PR noted as the objective status on 2 consecutive evaluations at least 4 weeks apart. A patient that has a confirmed response (Cohort 2) is considered a treatment “success”. The following 2-stage Simon Optimal MinMax design (see below) requires a maximum of 25 evaluable patients, and simultaneously discriminates between confirmed response rates of 5% vs. 25%.

16.15 Decision Rules for Cohort 2:

16.151 Final Analysis Decision Rule: Enroll 25 evaluable patients. If at least 4 patients have a success (at least 16%) among the 25 evaluable patients, this combination therapy would be considered worthy of further testing in this disease. If 3 or fewer patients have a success, this combination therapy will be considered negative and no further study would be warranted.

16.152 Stage 1 Decision Rule: After the first 15 patients entered into the trial become evaluable for the primary endpoint, a stage 1 analysis will be performed. If 1 or more patients have a success, the study will continue to full accrual. Otherwise, if 0 successes are observed, the study will be stopped early and the treatment will be considered ineffective in this patient population. Accrual will stop after we enroll the first 15 eligible patients to this cohort.

16.153 Power and Significance Level: This design has 90% power to detect a true success rate of 25%, with a significance level of 0.05 if the true success rate is 5%.

16.16 Over Accrual: If more than the target number of patients are accrued, the additional patients will not be used to evaluate the stopping rule or used in any decision making process.

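### Sections 16.12 and 16.14 count every eligible treated patient, yet 16.21 and 13.8 leave major treatment violators open to replacement. If treated non-responders were replaced, the type I error would pass the stated 0.09 in Cohort 1, and the stated 0.05 in Cohort 2 only near the worst case.

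*Combined protocol and SAP*

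**What the plan says.** **Who is evaluable.** Sections 16.12 (Cohort 1) and 16.14 (Cohort 2) use the same sentence: "All patients meeting the eligibility criteria who have signed a consent form and have begun treatment will be considered evaluable for the primary endpoint". Neither makes an exception for major violators. A success is a CR in Cohort 1 and a confirmed CR or PR in Cohort 2.

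**What the extra accrual is for.** Section 16.21 sets 25 evaluable patients per cohort and adds 5 per cohort "in order to account for ineligibility, cancellation, major treatment violation, or other reasons", for a maximum of 30 each.

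**What a major violation is.** Section 13.8 applies the term "if protocol requirements regarding treatment in cycle 1 of the initial therapy are severely violated that evaluability for primary end point is questionable". It then says: "The patient will go directly to the event-monitoring phase of the study".

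**What a cancel is.** Section 13.9 uses this term for a patient "if he/she is removed from the study for any reason before any study treatment is given".

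**Patients beyond target.** Under 16.16, "the additional patients will not be used to evaluate the stopping rule or used in any decision making process".

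**The concern.** Two of the reasons listed in 16.21 fit the evaluable definition. Ineligible patients and cancels fall outside it, so allowing for them is consistent. A major violator who is eligible and has begun treatment falls inside it. Extra accrual for that category makes sense only if such patients are not counted, which is the opposite of 16.12 and 16.14. The catch-all at the end of the list sets no limit on what else might qualify.

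The choice can affect the decision. With thresholds of 2 and 4 successes in 25, one patient more or less can settle the result. Because 16.16 bars patients beyond the target from decisions, whether a violator counts also fixes which later patient enters the 25, and in Cohort 2 which patients make up the first 15 evaluable at stage 1.

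The likely direction is upward. A major violator goes directly to event monitoring and so leaves the test schedule. The first scheduled imaging is Cycle 3 Day 1 (Section 4.0, footnote 5), and a Cohort 2 success needs two consecutive evaluations at least 4 weeks apart. Someone removed for a cycle 1 violation is therefore unlikely to have a success on record. Excluding such patients would mainly remove non-successes and make the go rules easier to meet than the stated error rates imply.

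**Working it through.** **Inputs**
- Cohort 1 (16.12, 16.131, 16.132): n = 25, positive if at least 2 CRs, null rate 0.02, target rate 0.15. Stated significance level 0.09, power 91%.
- Cohort 2 (16.14, 16.151–16.153): stage 1 of 15 patients, stop at 0 successes; positive if at least 4 of 25; null rate 0.05, target rate 0.25. Stated significance level 0.05, power 90%.
- Extra places (16.21): 5 per cohort. The number k used to replace treated non-responders is not given. I take k = 0 to 5.

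**Step 1. The plan's own figures (k = 0)**

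Cohort 1: alpha = 1 − 0.98^25 − 25 × 0.02 × 0.98^24 = 1 − 0.6035 − 0.3079 = 0.0886. Power = 1 − 0.85^25 − 25 × 0.15 × 0.85^24 = 1 − 0.0172 − 0.0759 = 0.907. Both match the plan.

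Cohort 2: sum over stage 1 counts x ≥ 1 of P(X1 = x) × P(X2 ≥ 4 − x), with X1 ~ Bin(15, p) and X2 ~ Bin(10, p). At p = 0.05:
- x = 1: 0.3658 × 0.0115 = 0.0042
- x = 2: 0.1348 × 0.0861 = 0.0116
- x = 3: 0.0307 × 0.4013 = 0.0123
- x ≥ 4: 0.0055

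The total is 0.0336. At p = 0.25 the same sum gives 0.901. The power matches. The stated 0.05 is consistent as a nominal ceiling, and the exact alpha lies well below it.

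**Step 2. Replacing k treated non-responders**

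If k treated non-responders are dropped and k new patients enter, the same cutoff is in effect applied to 25 + k treated patients.

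Cohort 1: alpha(k) = 1 − 0.98^(25+k) − (25+k) × 0.02 × 0.98^(24+k). At k = 5: 1 − 0.5455 − 0.3340 = 0.1205.

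Cohort 2: the two-stage sum with the k extra patients placed either all in stage 2 (15, then 10 + k) or all in stage 1 (15 + k, then 10).

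| k | Cohort 1 alpha (stated 0.09) | Cohort 2 alpha, replaced in stage 2 / stage 1 (stated 0.05) |
|---|---|---|
| 0 | 0.0886 | 0.0336 |
| 1 | 0.0948 | 0.0380 / 0.0383 |
| 2 | 0.1011 | 0.0427 / 0.0433 |
| 3 | 0.1075 | 0.0476 / 0.0487 |
| 4 | 0.1140 | 0.0528 / 0.0544 |
| 5 | 0.1205 | 0.0582 / 0.0604 |

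**Step 3. Cross-check**

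Keep n = 25 and raise the null rate to p0/(1 − v), with v = k/(25 + k). At k = 5, v = 5/30, so the null rates become 0.02/(5/6) = 0.024 and 0.05/(5/6) = 0.06. The alphas are 0.1203 and 0.0590, in line with the table.

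**Step 4. The neutral case**

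If violation is unrelated to response and the null rates describe non-violators, the 25 counted patients still respond at 0.02 or 0.05. Alpha then stays at 0.0886 and 0.0336.

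**The case against.** The strongest reply is that 16.21 only sets maximum accrual. It says the extra patients allow for certain losses and does not say that treated patients leave the denominator. The explicit analysis rule is in 16.12 and 16.14, and read alone it already gives the right answer. That is fair, and it rules out saying that the plan prescribes replacement of treated non-responders. But 13.8 puts the violator's evaluability for this very endpoint in doubt, and nothing ranks the sections, so the ambiguity stands.

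A reader might infer that replacement pushes both cohorts above their stated levels. The figures do not support that. Cohort 2 stays below 0.05 with up to three replaced, and the five places must also cover ineligibility, cancellation and other losses, so four or five is near the worst case. In Cohort 1 a single replacement gives 0.0948, which still rounds to 0.09.

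A reader might also infer that patients who could not tolerate the combination would be removed through this route, for example after early dose holds. The documents point the other way. Section 8.0 requires its modifications to be followed strictly for the first two cycles, so a hold made under 8.2 or 8.3 is compliance. Patients who stop for adverse events go to Observation under 13.3, and 16.31 keeps everyone who started treatment in the adverse event analysis.

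Finally, that dropped patients are mostly non-responders is an inference. The defining event lies in cycle 1, before any scheduled response scan. It is a reasonable inference, because these patients leave the imaging schedule and 13.8 sets no deadline for confirming a violation, but it remains an assumption.

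**Conclusion.** The conflict between 16.12/16.14 on one side and 16.21/13.8 on the other is real and should be resolved before the analysis. Its effect on the error rates is conditional: it arises only if 13.8 and 16.21 are followed, and if those replaced are non-responders who belong in the null rate. On those assumptions Cohort 1 exceeds its stated level from the first replacement, clearly so from the second, and reaches about 0.12 at five. Cohort 2 has slack and exceeds its stated level only at four or five, reaching about 0.06. The number of violators is assumed throughout. Confidence is high for the conflict in wording and lower for the size.

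**What to change.** 1. In 16.21, strike the last two reasons (major treatment violation and the catch-all), so that the extra accrual covers only ineligible patients and cancels.
2. In 13.8, 16.12 and 16.14, state that an eligible patient who received any study drug stays in the denominator and counts as a non-success if no qualifying response is recorded.

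The design then keeps its own error rates (alpha 0.0886 and 0.0336, power 0.907 and 0.901), provided the null and target rates describe all eligible treated patients. Sample size does not change.

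The cost is a protocol wording change and a reported response rate that may be slightly lower. If the target rate were meant for non-violators only, each violator counted as a failure would also cost some power: in Cohort 1, from 0.907 to 0.894 with one and 0.880 with two.

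One limit remains. Ineligibility under 13.7 can be discovered after treatment has started, so this change does not close every route to a post-treatment exclusion. That route does at least rest on the patient's status at registration.

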11.0 Treatment Evaluation Using RECIST Guideline

NOTE: This study uses protocol RECIST v1.1 template dated 2/16/2011. See the footnote for the table regarding measurable disease in Section 11.44, as it pertains to data collection and analysis.

Response and progression will be evaluated in this study using the new international criteria proposed by the revised Response Evaluation Criteria in Solid Tumors (RECIST) guidelines (version 1.1). Changes in the largest diameter (unidimensional measurement) of the tumor lesions and the short axis measurements in the case of lymph nodes are used in the RECIST guideline.

11.1 Schedule of Evaluations: For the purposes of this study, patients should be reevaluated every 6 weeks to 18 weeks after treatment initiation, then every 12 weeks until end of active study treatment (54 weeks). In addition to a baseline scan, confirmatory scans should also be obtained at least 4 weeks following initial documentation of objective response.

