13.0 Treatment/Follow-up Decision at Evaluation of Patient

- 13.1 Patients who are CR, PR, or SD will continue treatment per protocol.
- 13.2 Patients who develop PD while receiving therapy or refuse treatment or choose alternative therapy will go to the event-monitoring phase per Section 18.0 and be followed every 180 days for a maximum of 3 years from study registration. (See exceptions in 13.5 and 13.6.)
- 13.3 Patients who go off protocol treatment for reasons other than those listed in Section 13.2 above (e.g., adverse events, other complicating disease) will go to Observation and will follow the test schedule (Section 4.0) every 84 days for a maximum of 3 years from study registration. If they progress or choose alternative therapy while in Observation, they will go to the event-monitoring phase.
- 13.4 OBSERVATION: The study treatment period is 54 weeks (19 cycles). Patients who are receiving clinical benefit (i.e., in CR or PR or SD) and who are tolerating treatment at the end of the study treatment period may continue on therapy for an additional 12 months. After study treatment has been discontinued, they should be observed every 12 weeks until PD or a maximum follow-up of 3 years from study registration. Once the patient has PD during observation, they will be followed in the event-monitoring phase for a maximum follow-up of 3 years from study registration (see Section 18.0). Subsequent treatment is at the discretion of their attending physician. NOTE: If the patient continues for an additional 12 months of treatment beyond the initial 54 weeks, the patient should follow the same test schedule, per protocol, as is done during the initial 54-week period.
- 13.5 Patients who develop PD in the CNS may receive radiotherapy and continue treatment on study after completion of radiotherapy. **NOTE: Both lenvatinib and pembrolizumab should be withheld for a minimum of 3 days prior to radiation and for 3 weeks after radiation.**

13.6 Accumulating evidence indicates a minority of patients treated with immunotherapy may derive clinical benefit despite initial evidence of PD. Patients receiving treatment in this study will be permitted to continue treatment beyond initial PD, if the initial PD happens in the first 12 weeks post-registration (by RECIST 1.1), as long as they meet the following criteria:

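### The 6-month follow-up planned for the last patient is less than half of the 54-week response schedule, and neither primary endpoint has an assessment window or data cut

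*Combined protocol and SAP*

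**What the plan says.** **Timing.** Section 16.2 sets the size and pace: "Therefore, maximum accrual is 60 patients for this trial (30 for each Cohort"), "We expect to accrue about 3 patients per month to this trial", and so "the accrual period for this Phase II study is expected to be about 20 months". Section 16.22 continues: "We anticipate that the study will take approximately 3 years to complete". It then adds: "This allows a 6 month follow-up for the final patient enrolled, along with data entry, data clean-up, and analysis". Section 16.7 says: "The final analysis is expected to take place around 36 months after the study begins", and gives the same month as the expected completion time of the primary endpoint.

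**Response assessment.** Section 11.1 schedules scans every 6 weeks to week 18, "then every 12 weeks until end of active study treatment (54 weeks"). The test schedule footnote on imaging agrees: day 1 of cycles 3, 5, 7, 11, 15 and 19, which is weeks 6, 12, 18, 30, 42 and 54. Section 13.4 sets a treatment period of 54 weeks, with an optional further 12 months for patients who are benefiting.

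**Primary endpoints.** Section 16.12 (Cohort 1, complete response rate) and Section 16.14 (Cohort 2, confirmed response rate) count every eligible, consented patient who has begun treatment as evaluable. Neither says by when a response must be seen.

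**Longer follow-up.** Under Section 13.2, patients who progress or change therapy are to "be followed every 180 days for a maximum of 3 years from study registration". Sections 13.3, 13.4 and 18.1 use the same 3-year limit.

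**The concern.** The only minimum follow-up in the plan is 6 months, or about 26 weeks. A patient with that much follow-up has had the scans at weeks 6, 12 and 18 but not those at weeks 30, 42 and 54. With no window in the endpoint definition, the date of the data cut decides which responses count.

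This matters most for the binary primary endpoints. Everyone who starts treatment is in the denominator, so a patient whose first complete response would have been seen after the cut is scored as a failure. The Cohort 1 decision turns on 2 complete responses in 25, so one missed response can change it. In an open-label single-arm trial, the cut should also not be left to be chosen once responses are visible.

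Separately, a study described as 3 years long cannot contain 3 years of follow-up for patients who enter over 20 months. The plan does not say whether PFS and OS will be updated after month 36.

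**Working it through.** **Inputs.** 60 patients at most, 3 per month, 6 months for the last patient, about 3 years in total (16.2); final analysis at about month 36 (16.7); last scheduled response scan at week 54 (11.1, 13.4); 50 patients in the decision rules, 25 per cohort (16.21), with over-accrual excluded from decisions (16.16). Assumptions: uniform accrual and no pause at the Cohort 2 stage 1 analysis.

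**The plan's own figures.**
- Accrual: 60 / 3 = 20 months, as stated.
- Cohort 1 rule (at least 2 of 25): probability 0.089 at a true rate of 2% and 0.907 at 15%, against the stated 0.09 and 91%.

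**Does 36 months cover week 54?**
- 54 weeks = 54 × 7 / 30.44 = 12.4 months.
- Last patient at week 54: 20 + 12.4 = month 32.4. With a confirmatory scan 4 weeks (0.9 months) later: month 33.3.
- Available after last enrolment: 36 − 20 = 16 months, against 12.4 needed. The total is sufficient.

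**What would a cut at 6 months after last enrolment do?** The cut falls at 20 + 6 = month 26. A patient has less than 54 weeks of potential follow-up if enrolled after month 26 − 12.4 = 13.6.
- Accrual over the full 20 months: (20 − 13.6) / 20 = 32%, about 19 of 60.
- Only the first 50 patients used, all evaluable and enrolled by month 50 / 3 = 16.7: (16.7 − 13.6) / 16.7 = about 19%, or 9 of 50.
- Accrual rate: at 2.5 per month (24 months) the first figure is 6.4 / 24 = 27%; at 3.5 per month (17.1 months) it is 37%.

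| Data cut | Share below 54 weeks (20-month accrual) |
|---|---|
| month 26 | 32% |
| month 30 | 12% |
| month 32.4 or later | essentially none |

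**Effect on the Cohort 1 decision (illustration only).** The documents give no timing for complete responses, so the share L first seen between 6 months and week 54 is an assumption, taken as 25% to 75%. Observed rate = 15% × (1 − L × share of late responses lost); power is the binomial probability of at least 2 in 25. The table uses the 32% case and a month-26 cut.

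| Timing of late responses | Share of late responses lost | Observed rate, L = 25% to 75% | Power |
|---|---|---|---|
| spread evenly from 6 months to week 54 | 0.32 / 2 = 0.16 | 14.4% to 13.2% | 89% to 86% |
| all at the week-54 scan | 0.32 | 13.8% to 11.4% | 88% to 80% |

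In the 19% case the loss is smaller: power stays between 90% and 85% over the same assumptions.

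**Three-year follow-up.** The last patient reaches 3 years from registration at 20 + 36 = month 56, 20 months after the stated end. At a month-36 cut, potential follow-up runs from 16 to 36 months with a median of 26, so essentially every patient is still short of 3 years.

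**The case against.** The strongest reply is that the plan never sets a data lock at month 26. Section 16.22 says what the duration allows, and Section 16.7, the only place that dates the primary endpoint, says about month 36. On that reading no patient is short of week 54. This stands in part: the month-26 cut is one reading, and the 19% to 32% depends on it. But Section 16.22 divides the time after last enrolment into 6 months of follow-up and, by subtraction, 16 − 6 = 10 months of data work. Nothing else in the plan requires longer follow-up before the analysis.

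Three stronger readings are tempting, and the documents do not support them.

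- A reader might infer that a 3-year study is too short for the 54-week schedule. It is not: week 54 for the last patient falls at month 32.4.
- A reader might infer that about a third of responses or events would be lost. The 32% is the share of patients with incomplete potential follow-up at an assumed cut. Those who have already responded, progressed or died lose nothing for the response endpoint. The figure also falls to about 19% if the 50 decision patients enter by month 16.7.
- A reader might infer that PFS and OS at month 36 are invalid. Three years is a maximum, these are secondary endpoints estimated by Kaplan-Meier, and administrative censoring is handled. They would be immature, not wrong.

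**Conclusion.** The point holds in a limited form. The stated 6-month minimum does not match the protocol's own response schedule, and the missing window and cut date leave the primary result dependent on when data are taken. If the cut came at about month 26, 19% to 32% of patients would have incomplete response follow-up. The bias in the response rates could only run against the treatment. Its size cannot be settled from the documents; under the assumed timings Cohort 1 power falls from 91% to somewhere between 90% and 80%. If the cut came at month 32.4 or later, with accrual at 3 per month, the problem would not arise. The planned 36 months allows this, so the change should be made. The stated study duration also needs correcting, since follow-up as specified ends at about month 56.

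**What to change.** 1. **Sections 16.22 and 16.7:** replace the 6-month minimum with a primary data cut once every evaluable patient has reached the week-54 assessment, plus any confirmatory scan, or has earlier progressed, died or started alternative therapy. Patients who stop treatment for other reasons are counted through their observation scans to week 54. At 3 patients per month the cut falls at about month 32.4 to 33.3.
2. **Sections 16.12 and 16.14:** define the primary endpoint as response through week 54. Describe later responses, including those during the optional extra 12 months, separately.
3. **Section 16.22:** state that follow-up to 3 years from registration ends at about month 56. Label PFS and OS at month 36 as interim Kaplan-Meier estimates, to be updated when follow-up ends.

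**Cost:** changes of wording and one later update of PFS and OS. About 3 months (36 − 33.3 = 2.7, or 36 − 32.4 = 3.6) remain for cleaning and analysis before month 36, instead of 10. At 2.5 patients per month accrual takes 24 months and the last week-54 scan falls at month 36.4, so the analysis would slip slightly past month 36.
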